#### Statistical Analysis Plan

Final analysis

Final 1.0 of 26APR2024

	Disease status at roll-over						
Endpoint	CRmin	CR	DC - no CR	Treatment failure	Flare after CRmin	Overall	
Period2,, n	Х	Х	Х	Х	Х	Х	
Follow-up	Х	Х	Х	Х	Х	Х	
Time to CR c							
Period 1			Х	Х	Х	Х	
Period2,, n	Х	Х	Х	Х	Х	Х	
Follow-up	Х	Х	Х	Х	Х	Х	
Time to CRmin c							
Period 1		Х	Х	Х	Х	Х	
Period2,, n	Х	Х	X	Х	Х	Х	
Follow-up	Х	Х	Х	Х	Х	Х	
Time to CRoff c							
Roll-over phase	Х						
Period 1		Х	Х	Х	Х	Х	
Period 2,, n	Х	Х	Х	Х	Х	Х	
Follow-up	Х	Х	Х	Х	Х	Х	
NCPD°	Х	Х	Х	Х	Х	Х	
Proportion flare after CRmin c							
Overall d	Х	Х	Х	Х	Х	Х	
Roll-over phase	Х						
Period 1		Х	Х	Х	Х	Х	
Period 2,, n	Х	Х	Х	Х	Х	Х	
Follow-up	Х	Х	Х	Х	Х	Х	
Time to flare after CRmin c							
Roll-over phase	Х						
Period 1		Х	Х	Х	Х	Х	
Period 2,, n	Х	Х	Х	Х	Х	Х	
Follow-up	Х	Х	Х	Х	Х	Х	
Number of flares c	Х	Х	Х	Х	Х	Х	
Proportion treatment failure c	Х	Х	Х	Х	Х	Х	
PDAI c						Х	
QoL, C-GTI						Х	

CONFIDENTIAL AND PROPRIETARY

System Version: 1.0, Status: Approved, Document ID: VV-TMF-172580

SGS	Statistical Analysis Plan	
ARGX-113-1905	Final analysis	Final 1.0 of 26APR2024
	Disease status at roll-ove	er

		Disease status at roll-over					
Endpoint	CRmin	CR	DC - no CR	Treatment failure	Flare after CRmin	Overall	
c Analysis done for a	c Analysis done for all participants (PV+PF) as well as for PV participants						
d Overall = during the	ing the roll-over phase (if applicable), during any treatment period or during the						
follow-up phase							

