#### 4.1.2.1 **PROPORTION OF PARTICIPANTS WHO ACHIEVE CRMIN AND CROFF**

The proportion of participants who achieve CRmin in 1905 (as assessed by the investigator) will be derived within each treatment period, within the follow-up phase and over the entire study (ie, whether the participant achieves the status during at least one treatment period or during the follow-up phase).

Missing values for the below reasons, will be imputed as follows:

- all CR assessments missing: CRmin = non-response
- CRmin never ticked: CRmin = non-response
- CRmin is ticked but date of CRmin is missing: date for CRmin will be imputed by disease assessment visit date

Proportions will be calculated overall and by subgroup of disease status at roll-over.

Similar analyses as described above for CRmin will be performed for CRoff.

For the roll-over phase of participants who enter study 1905 on CRmin, only the proportion of participants achieving CRoff will be derived, as participants already achieved CRmin before the start of 1905. Participants entering 1905 on CRoff will be excluded from this calculation.

For the follow-up phase, participants who start the follow-up phase on CRmin (or CRoff) will be excluded from this calculation.

SGS	Statistical Analysis Plan	
ARGX-113-1905	Final analysis	Final 1.0 of 26APR2024

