#### 4.1.2.4 **PROPORTION OF PARTICIPANTS WITH FLARE AFTER CRMIN**

For participants who achieve CRmin (in 1904 or 1905), the proportion of participants who experience a flare in 1905 after CRmin (as assessed by the investigator) will be derived within the roll-over phase (flare after CRmin in 1904), within each treatment period (flare after CRmin within the treatment period), within the follow-up phase (flare after CRmin prior to follow-up phase) and over the entire study (ie, whether the participant achieves the status during the roll-over phase, during at least one treatment period or during the follow-up phase).

For the follow-up phase, participants who start the follow-up phase not on CRmin or CRoff will be excluded from this calculation.

Proportions will be calculated overall and by subgroup of disease status at roll-over.

SGS	Statistical Analysis Plan	
ARGX-113-1905	Final analysis	Final 1.0 of 26APR2024

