### 4.1.3 Presentation of results

#### 4.1.3.1 **PROPORTION OF PARTICIPANTS WHO ACHIEVE CRMIN AND CROFF**

Frequency tabulations will be provided of the percentage (with 95% exact confidence interval) of PV participants and all participants (PV+ PF) achieving CRmin within each treatment period, within the follow-up phase and over the entire study. The table will be repeated by disease status at roll-over.

Similar tables will be provided for the percentage of participants achieving CRoff.

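### Overall CRoff proportion has two definitions in the SAP: the list carried over from CRmin in 4.1.2.1 omits the roll-over phase, while footnote d of 4.1.3.7 includes it

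*SAP*

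**What the plan says.** SAP 4.1.2.1 sets the rule for CRmin. It is derived by treatment period, in follow-up, and "over the entire study (ie, whether the participant achieves the status during at least one treatment period or during the follow-up phase". CRoff is then added in one line: "Similar analyses as described above for CRmin will be performed for CRoff".

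The next paragraph deals with the roll-over phase of participants who enter on CRmin. For them "only the proportion of participants achieving CRoff will be derived, as participants already achieved CRmin before the start of 1905", and those who enter on CRoff are left out. It does not say whether this result feeds the whole-study figure. For follow-up, "participants who start the follow-up phase on CRmin (or CRoff) will be excluded from this calculation".

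SAP 4.1.3.1 describes the tables as the percentage "achieving CRmin within each treatment period, within the follow-up phase and over the entire study", with similar tables for CRoff. Again the roll-over phase is not listed.

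The overview table in SAP 4.1.3.7 gives Proportion CRoff an Overall row and a separate Roll-over phase row. The Overall row carries footnote d, under which the status counts if reached during "the roll-over phase (if applicable), during any treatment period or during the" follow-up phase.

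For flare after CRmin, SAP 4.1.2.4 names the roll-over phase inside its whole-study rule: "whether the participant achieves the status during the roll-over phase, during at least one treatment period or during the follow-up phase".

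**The concern.** The roll-over phase is where participants who enter on CRmin are observed without efgartigimod and may have prednisone tapered further at the investigator's discretion. Under SAP 2.2.1 they have no treatment period 1. They enter a treatment period only if they flare and restart IMP. If they are never treated, their roll-over phase runs to the Week 52/EoT/ET visit.

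Take such a participant who reaches CRoff and stays there. No treatment period exists in which the CRoff could count, and starting follow-up on CRoff excludes the person from the follow-up calculation. Read literally, 4.1.2.1 makes this participant an overall non-responder. Another CRmin entrant who flares, is retreated and then reaches CRoff is a responder. Footnote d counts both.

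The figure appears in tables 14.2.1.1.3 and 14.2.1.1.4, both marked for topline results, with exact 95% confidence intervals. SAP 6.1 lists the CRoff proportion as an endpoint added to the protocol's set, so the SAP is its only definition. Under SAP 1.7 only ADSL, ADAE and ADLB are independently programmed. The efficacy outputs are reviewed, so double programming would not bring the two readings to light.

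**Working it through.** The plan gives no figure for this proportion, so there is nothing to reproduce. The check applies both rules to each possible pattern and then sizes the gap.

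**Step 1: classification.**

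| CRoff reached in | 4.1.2.1 list, read literally | Footnote d |
|---|---|---|
| Roll-over phase only | no | yes |
| Roll-over phase and a later treatment period | yes | yes |
| Treatment period only | yes | yes |
| Follow-up only | yes | yes |
| Never | no | no |

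The rules differ in the first row only.

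**Step 2: formula.** By default SAP 2.4.1 uses all participants in the analysis set, per treatment, as the denominator, so uncounted participants remain as non-responders. With p the share entering on CRmin and r the share of those whose only CRoff is in the roll-over phase, gap = p × r.

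**Step 3: inputs.**
- N = 213, the approximate maximum in SAP 1.3.
- p and r are not in the documents. Each is assumed at 10%, 30% and 50%.
- CRoff in all other participants is assumed at 10%. This affects the level of both figures but not the gap.
- No allowance is made for participants who entered on CRoff.

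**Step 4: gap in percentage points**, using whole participants (CRmin entrants m = 21, 64 and 106 of 213).

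| | r = 10% | r = 30% | r = 50% |
|---|---|---|---|
| p = 10% | 2/213 = 0.9 | 6/213 = 2.8 | 10/213 = 4.7 |
| p = 30% | 6/213 = 2.8 | 19/213 = 8.9 | 32/213 = 15.0 |
| p = 50% | 11/213 = 5.2 | 32/213 = 15.0 | 53/213 = 24.9 |

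**Step 5: middle case with exact (Clopper-Pearson) 95% intervals.** There are 64 CRmin entrants, 19 of them with CRoff in the roll-over phase only, and 149 others, of whom 10% (15) reach CRoff.
- 4.1.2.1 list: 15/213 = 7.0% (4.0 to 11.3).
- Footnote d: (15 + 19)/213 = 34/213 = 16.0% (11.3 to 21.6).
- CRmin-at-entry subgroup: 0/64 = 0.0% (0.0 to 5.6) against 19/64 = 29.7% (18.9 to 42.4), if none of the 64 reaches CRoff in a later treatment period or in follow-up.

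**The case against.** The best defence is that the texts can be reconciled. The list in 4.1.2.1 sits in a sentence about CRmin, where omitting the roll-over phase is right because these participants had already reached CRmin. A similar analysis need not be an identical one. The same section asks for CRoff in the roll-over phase. The qualifier in footnote d then reads naturally as not applicable to CRmin and applicable to CRoff. The contrast with 4.1.2.4 is weaker than it looks, because flare can occur in the roll-over phase and its rule had to name that phase.

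Most of this stands. The likely cause is wording carried over from CRmin, and footnote d is probably the intended rule. It does not remove the problem: neither 4.1.2.1 nor 4.1.3.1 says that roll-over-phase CRoff enters the whole-study figure, and the only list they give leaves that phase out.

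Two further points also stand. Roll-over-phase CRoff has its own row, so no event disappears. The wording of table footnotes a and b is not visible in the text available to me, and footnote b marks the Overall and Roll-over cells for CRmin entrants under Proportion CRoff. It may bear on who is excluded, so I do not rely on it and cannot say what it settles.

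**Conclusion.** The point holds as an inconsistency in a descriptive topline figure. It affects only participants who enter on CRmin and whose sole CRoff is in the roll-over phase. On the assumed ranges the gap is about 1 to 25 percentage points overall and larger within the CRmin-at-entry subgroup. No single value can be defended, since neither share is documented.

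A reader might infer more than the documents support:
- That the SAP prescribes a wrong rule which programmers will follow. It contains two statements, and one of them matches the apparent intent.
- That the roll-over phase is a main source of CRoff events. Tapering there is optional, participants in treatment periods can also reach CRoff, and no rates are given.
- That everyone who tapers to zero is classified differently. CRoff also requires healed lesions and at least 8 weeks off prednisone, and anyone who reaches CRoff again in a later treatment period counts under both rules.
- That a trial conclusion turns on it. All efficacy analyses are descriptive and no hypothesis is tested.

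It is still worth correcting, because one of the two definitions would report sustained remission off therapy as non-response.

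**What to change.** In SAP 4.1.2.1 and 4.1.3.1, state that overall CRoff counts achievement in the roll-over phase, any treatment period or the follow-up phase. This agrees with footnote d and with the approach in 4.1.2.4. Leave the CRmin rule as it is.

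In the same place, state whether participants who entered on CRoff are excluded from the overall denominator. The section removes them from the roll-over-phase calculation but says nothing about the overall one, and SAP 2.5 groups them with CRmin entrants. Check the wording against table footnote b.

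The cost is a sentence or two in each section, recorded as a change to the final SAP (6.3). No new data or analysis is needed, and no protocol amendment, because the CRoff proportion is defined only in the SAP.

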#### 4.2 PHARMACOKINETICS

PK data will be presented for the Safety analysis set.

#### 4.2.1 Available data

Blood samples will be collected for the determination of efgartigimod concentration at the time points indicated in the schedule of activities (see section 9.2). Sampling will be done predose on IMP administration visits (within 2 hours before IMP).

PK data obtained during off-treatment subperiods from participants who achieved CRmin (ie, no longer receiving weekly administrations of IMP) will not be included in the descriptive statistics.

In addition, following PK samples will be excluded from the descriptive statistics:

- When PK samples are taken outside the visit windows. The study visit windows are ±2 days, i.e. if PK sample is not within last IMP+7 days ± 2 days.
- When a predose sample is taken after IMP administration.
- When the IMP administration prior to the scheduled PK sample is missed (not applicable for Day 1 of a new treatment period).

A remark with reason for exclusion of the timepoint will be added in the appropriate listing.

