- ^b In case of suspected new lesions as reported by the participants, AEs, flare, or other safety reasons, participants should come to the clinic. This may require an unscheduled visit. Depending on the reason for the visit, different assessments need to be performed. Refer to Section 8 for more information. Participants with new lesions or flare after achieving CR should return to weekly on-site visits. Participants with flare who had achieved CRmin or CRoff should switch to the visit schedule outlined in Table 2.
- ^c Follow-up 1 will be the EoS visit for participants who ended treatment before W49 or 4 weeks before ET. Both follow-up visits will be required only for participants who continue to receive efgartigimod PH20 SC for at least 1 visit between W49 and W52 or during the last 4 weeks before ET.

^d Study visit windows are ± 2 days during the treatment period and ± 3 days for the follow-up visits.

^e Weight will be measured and BMI will be calculated accordingly, at the rollover visit, at W26 (or the next on-site visit if W26 does not coincide with an on-site visit) and W52. Weight will also be measured if there has been an obvious change since the last measurement.

^f Assessment or procedure will be completed predose at visits when IMP is administered.

^g The ECG will be recorded at baseline, every 3 months while receiving efgartigimod PH20 SC treatment, at CRmin (or the next on-site visit if CRmin is achieved during a week without an on-site visit), and at EoS. The ECG (heart rate, PR, QT, and QRS interval) will be read centrally, and QTcF and QTcB will be calculated. The ECG will be recorded only at baseline and EoS in participants not receiving efgartigimod. Additional ECGs may be performed at the discretion of the investigator during unscheduled visits.

- ^h A complete physical examination will be performed at each on-site visit. Vital sign measurements include systolic and diastolic blood pressure, heart rate, and body temperature.
- ⁱ Urinalysis will be performed by dipstick method and will include specific gravity, pH, protein, glucose, ketones, blood, bilirubin, urobilinogen, nitrite, leukocyte esterase, and microscopic examination (if blood or protein is abnormal).
- ^j A urine pregnancy test will be performed locally and at least once every 4 weeks.

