- ^k Clinical blood laboratory tests will include hematology and blood chemistry at all visits. The hematology profile includes hemoglobin, hematocrit, MCV, RBC count, platelet count, and WBC count with differential. The blood chemistry profile includes sodium, potassium, calcium, HbA1c, creatinine, creatinine clearance, BUN, ALT, AST, total bilirubin, GGT, CRP, ALP, LDH, LDL-C, uric acid, total protein, and albumin.
- ¹ PK and PD (total IgG and IgG subtypes) samples will be taken every 4 weeks as long as the participant is receiving efgartigimod PH20 SC treatment (until CRmin or the next on-site visit) and 4 weeks after CRmin (or the next on-site visit; this also applies if the participant achieved CRmin in ARGX-113-1904) or EoT. Blood samples will be taken predose (within 2 hours before the start of IMP administration during visits when IMP is administered).
- ^m At unscheduled visits, blood samples for PK will only be taken if IMP is administered.
- ⁿ Blood samples will be taken to test for immunogenicity to efgartigimod in serum and rHuPH20 in plasma every 4 weeks while the participant is receiving efgartigimod PH20 SC treatment (until CRmin or the next on-site visit) and 4 and 8 weeks after CRmin (or the next 2 on-site visits; this also applies if the participant achieved CRmin in ARGX-113-1904) or EoT. NAb will be tested for all confirmed positive immunogenicity samples.
- ° Questionnaires are to be completed before any other assessment.
- ^p Disease assessment parameters include DC, EoC, CR, CRmin, CRoff, flare, and treatment failure. Participants who have achieved CR and have new lesions should come to the clinic for an unscheduled visit for disease assessment.
- ^q Samples for lymphocyte populations will be taken at selected sites only: optionally at on-site visits at W13 (±2 weeks), W26 (±2 weeks), W39 (±2 weeks), W52 (±2 weeks) or EoT/ET and EoS, and mandatory at on-site visits at W52 (±2 weeks) or EoT/ET and EoS for participants in CRmin or CRoff.
- ^r The GTI assessment will be performed at visit 1, W26 (or the next on-site visit), and W52.
- ^s Participants and/or their caregivers will be invited to receive at least 1 refresher training for self-administration, or caregiver-supported administration of IMP. Training will continue until deemed successfully completed by authorized staff.

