- ^t Efgartigimod PH20 SC will be administered weekly at a dose of 1000 mg until CRmin. For IMP administrations between the scheduled site visits, the participant can choose between self-administration (if training successfully completed), home nurse visits, or return to the trial site for the SC injection only. Participants who have achieved CRmin or CRoff and are currently not in flare will be observed every 4 weeks without any further IMP administration until flare or EoS. Only for on-site visits and home nurse visits, participants should be followed up for safety monitoring for at least 1 hour after the first IMP administration, or followed by 15 minutes of observation for subsequent administrations and released according to their clinical status. The last planned IMP administration is at W52. If the participant withdraws from the study, efgartigimod PH20 SC will not be administered.
- ^u Prednisone dose tapering will begin 2 weeks after achieving CR or 4 weeks after sustained EoC (thus, no new lesions have developed for a minimum of 6 weeks and approximately 80% or more of lesions have healed).

Table 2:Schedule of Activities for ARGX-113-1905 for Participants Not in CR at Rollover From ARGX-113-1904, or
Participants With Flare after CRmin or CRoff in ARGX-113-1905

Trial period	V1 ^a	Observational visits	IMP admin only visit	Observati	EoT/ET		Follow-up		
Visit Number		Weekly on-site visits until CR ^b	Weekly home or on-site visits until CRmin ^c	On-site visits every 4 weeks until CRmin	On-site visits every 4 weeks until W52	W52		Safety follow-up 1	Safety follow-up 2
Trial Week	Rollover ^a	V1 + 7x	CR until CRmin	CR until CRmin	After CRmin until W52	W52	UNS ^d	EoT/ET + 4 weeks ^e	EoT/ET + 8 weeks EoS ^e
Assessment/Procedure	±0 days		±2	days ^f		±2 days		±3 (lays ^f
Informed consent	Х								
Inclusion/exclusion criteria	X								
Weight ^g	Х	X ^g		X ^g	X ^g	Х			
ECG ^{h,i}	X	Х		Х	Х	X		Х	Х
Physical examination and vital signs ^{i,j}	X	Х		Х	X	Х	X	X	Х
Urinalysis ^{i,k,l}	X	Х		Х	Х	X	X ^d	Х	Х
Urine pregnancy test ^{i,m}	Х	Х		Х	Х	X	X ^d	X	Х
Vaccination antibodies ^{i,1}	Х	X		Х	Х	X	X ^d	X	X
Blood sampling									
 Clinical chemistry and hematology^{i,l,n} 	X	Х		Х	X	Х	Xd	Х	Х
 anti-Dsg-1 and anti- Dsg-3 antibodies^{i,1} 	X	X		X	X	X	X ^d	Х	Х

Trial period									
	V1 ^a	Observational visits	IMP admin only visit	Observati	EoT/ET		Follow-up		

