#### Table 1: Phase, period and subperiod definition

Document template OTH.STAT.010 v3

CONFIDENTIAL AND PROPRIETARY

System Version: 1.0, Status: Approved, Document ID: VV-TMF-172580

SGS	Statistical Analysis Plan	
ARGX-113-1905	Final analysis	Final 1.0 of 26APR2024

Treatment period 1 is only applicable for participants who did not achieve CRmin or CRoff in 1904

Treatment	Treatment period 1 b,c	On-treatment 1	Earliest of (date of signing the informed consent form (ICF) of study 1905 and date of roll-over), with 00:00 added as time part a .	For the participants with off- treatment 1 subperiod : last IMP administration date/time in treatment period 1. For other participants: Date of week 52/EoT/ET visit, with 23:59 added as time part.
			1	For participants who don't have a week 52/EoT/ET visit: date of last contact, with 23:59 added as time part.
		Off-treatment 1	administration date/time in treatment period 1	For the participants with a next treatment period: first IMP administration date/time in next treatment period – 1 minute.
			+ 1 minute	For other participants:
			Date of week 52/EoT/ET visit, with 23:59 added as time part.	
			For participants who don't have a week 52/EoT/ET visit: date of last contact, with 23:59 added as time part.	
	Treatment n	eriod 2 is applicab	le for participants with	flare after CRmin in the roll-over

Treatment period 2 is applicable for participants with flare after CRmin in the roll-over phase or in treatment period 1 and who re-initiate IMP administration

Treatment period 2 °	On-treatment 2	First IMP administration date/time in treatment period 2	For the participants with off- treatment 2 subperiod : last IMP administration date/time in treatment period 2.
			For other participants:
			Date of week 52/EoT/ET visit, with 23:59 added as time part.
			For participants who don't have a week 52/EoT/ET visit: date of last contact, with 23:59 added as time part.

Page 18 of 84

SGS	Statistica	al Analysis Plan		
ARGX-113-1905	F	inal analysis		Final 1.0 of 26APR2024
	Off-treatment 2	Last IMP administration date/time in treatment period 2	trea adm	the participants with a next tment period: first IMP ninistration date/time in next tment period – 1 minute.
		+ 1 minute For	For	other participants:
				e of week 52/EoT/ET visit, h 23:59 added as time part.
			wee last	participants who don't have a ek 52/EoT/ET visit: date of contact, with 23:59 added as e part.
Etc c				

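### The 7-day PK trough at a CRmin visit is dropped from the descriptive statistics although it meets the SAP's own trough rule, and the Day 1 exemption for retreatment periods does not work as written

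*SAP*

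**What the plan says.** Four parts of the plan bear on this.

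- **Dosing and order of procedures.** Protocol Table 1, footnote t: "Efgartigimod PH20 SC will be administered weekly at a dose of 1000 mg until CRmin". Footnote f: "Assessment or procedure will be completed predose at visits when IMP is administered". The synopsis says IMP is stopped on achieving CRmin.
- **Sampling.** Protocol Table 1, footnote l: "PK and PD (total IgG and IgG subtypes) samples will be taken every 4 weeks as long as the participant is receiving efgartigimod" treatment, up to CRmin or the next on-site visit, and again 4 weeks after CRmin. Protocol Table 2, footnote o, adds a sample at CR and restarts the 4-weekly schedule from there.
- **Subperiods.** SAP Table 1 ends the on-treatment subperiod, for participants who have an off-treatment one, at the "last IMP administration date/time in treatment period 1" (and likewise in later periods). Off-treatment starts one minute later. For other participants, on-treatment runs to the Week 52/EoT/ET visit. SAP 2.2.4 allocates PK to analysis visits by Table 5 only, that is, by subperiod.
- **PK exclusions.** SAP 4.2.1 begins by leaving out of the descriptive statistics "PK data obtained during off-treatment subperiods from participants who achieved CRmin", on the ground that weekly dosing has stopped. Three bullets follow. Bullet 1 excludes samples outside the visit window, "if PK sample is not within last IMP+7 days ± 2 days". Bullet 2 excludes predose samples taken after dosing. Bullet 3 excludes samples that follow a missed dose, but is "not applicable for Day 1 of a new treatment period".

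**The concern.** The off-treatment exclusion is evidently aimed at washout samples from participants who no longer receive weekly injections. A sample taken 7 days after a weekly dose is not washout. It has the same timing as every trough the table keeps. Because the boundary is set at the last injection and not at the end of its dosing interval, a sample can satisfy the SAP's definition of a valid trough and still be removed by subperiod. The removal applies only to CRmin achievers, in a secondary endpoint that is sampled sparsely.

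The Day 1 wording has a related problem. Bullet 3 shows that the SAP means to keep the predose sample at the start of a retreatment period, but two other rules in the same section still remove it.

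**Working it through.** The plan gives no figure to reproduce. The check applies its rules to a participant in CR at rollover.

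**Inputs.** Weekly doses from Week 0 with none missed. No dose at the CRmin visit. PK samples at Weeks 4, 8, 12 and so on (Protocol Table 1). Trough window of 7 ± 2 days, that is, days 5 to 9 after the last dose (SAP 4.2.1, bullet 1). Relative day in subperiod = sample date − first day of subperiod + 1 (SAP 2.2.2).

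**CRmin at the Week 4 visit.**
- The last dose is at Week 3, study day 22. The sample is on study day 29.
- Gap = 29 − 22 = 7 days, inside 5 to 9, so bullet 1 keeps it.
- Off-treatment starts on day 22, so the relative day is 29 − 22 + 1 = 8. This is the target day of Off-treatment Week 1 in SAP Table 5.
- The off-treatment exclusion therefore removes it. The next sample, 4 weeks after CRmin, comes 35 days after the last dose and fails bullet 1 in any case.

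**Other timings.** Post-dose troughs kept within the period:

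| CRmin at | Last dose | First PK sample after last dose | Kept as written | Kept if a 7-day trough counts |
|---|---|---|---|---|
| Week 3 | Week 2 | Week 4 (14 days) | 0 | 0 |
| Week 4 | Week 3 | Week 4 (7 days) | 0 | 1 |
| Week 6 | Week 5 | Week 8 (21 days) | 1 | 1 |
| Week 8 | Week 7 | Week 8 (7 days) | 1 | 2 |
| Week 12 | Week 11 | Week 12 (7 days) | 2 | 3 |
| Week 13 | Week 12 | Week 16 (28 days) | 3 | 3 |

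The subperiod rule changes the count only when CRmin falls on a scheduled PK visit. Samples outside days 5 to 9 already fail bullet 1. So among samples taken after the last dose of a period, the only ones the off-treatment exclusion removes beyond bullet 1 are those that meet the trough rule.

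**Can CRmin occur at Week 4?** Yes. CRmin needs 8 weeks at 10 mg/day, and time at that dose in ARGX-113-1904 counts. About 4 weeks there plus 4 weeks here gives 8.

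**Can it leave a retreatment period with no trough?** Not in the fastest case tried. Assume a 20 mg/day start and CR at Week 0. Tapering starts 2 weeks after CR: 17.5 mg at Week 2, 15 at Week 3, 12.5 at Week 4, 10 at Week 5. CRmin is then at Week 5 + 8 = Week 13 at the earliest, with troughs kept at Weeks 4, 8 and 12.

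**Day 1 of period 2 or later.** SAP Table 1 starts On-treatment 2 at the first injection of that period and ends the preceding off-treatment subperiod one minute before it. A predose sample therefore lies in that off-treatment subperiod, in someone who has achieved CRmin, and the opening exclusion applies. It also comes well beyond 9 days after the last dose, so bullet 1 applies. Bullet 3's exemption lifts only bullet 3. SAP Table 5, which governs PK, has a period-baseline (TPnB) row that these samples would fill. As written, it is empty for period 2 onward.

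**The case against.** The strongest case against is that little depends on this. PK is presented as descriptive statistics by period and time point, no hypothesis is tested, and the SAP specifies no exposure-response analysis. Excluded samples are still listed with the reason for exclusion, so nothing is irrecoverable. All of that stands, and it limits the weight of the point.

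Four stronger readings are tempting, and the documents do not support them.

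- **Every CRmin achiever loses a trough.** The protocol expects that CRmin may be reached in a week without an on-site visit. Dosing then stops, and the next sample fails the 7 ± 2-day window on its own merits.
- **Quick achievers contribute no post-dose PK.** This rule produces that result only for CRmin at the Week 4 visit, and only within that period. For CRmin at Weeks 1 to 3, the schedule and the window already leave no valid trough. Other periods or an unscheduled sample on a dosing day can still contribute.
- **PD at response is lost.** SAP 4.3.3 tabulates PD by overall visits as well as by subperiod, and the CRmin-visit IgG value stays in the overall tables. In the subperiod tables it appears as Off-treatment Week 1, which is a fair label.
- **The mean trough is biased.** Nothing in the documents shows this. Except for CRmin by Week 4, earlier troughs of the same participants remain.

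On Day 1, one can answer that the intent is clear from bullet 3, and that SAP 2.2.4 also allocates the last assessment before retreatment to the new period's baseline. Both are true. But allocating a sample to a row does not lift an exclusion from the statistics, and the literal rules still remove it.

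**Conclusion.** The point holds for PK. A sample at a CRmin visit that is also a scheduled on-site PK visit meets the SAP's trough rule and is nonetheless left out of the PK table. The cost is one trough per period per participant concerned. For participants in CR at rollover who reach CRmin at the Week 4 visit, it is the only scheduled post-dose trough of that period. The loss falls on responders alone.

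The Day 1 contradiction also holds: two rules remove what a third means to keep.

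The conclusion assumes that no injection is given at the CRmin visit, as dosing until CRmin and predose assessment imply. If one were given, the sample would precede it and stay on-treatment. It also assumes that weekly doses were not missed. The documents do not say how many participants are affected, and the number may be small. The consequence is modest, but the repair uses data already collected and should be made.

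**What to change.** In SAP 4.2.1, for PK only:

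1. Limit the off-treatment exclusion to samples taken more than 9 days after the last IMP.
2. Present samples within last IMP + 7 ± 2 days, with no intervening dose, under the matching on-treatment week. In the Week 4 example, day 29 is the target of On-treatment Week 4.
3. Apply the Day 1 (TPnB) exemption to both the off-treatment exclusion and bullet 1. Adding it to bullet 1 alone would not work, because the sample also sits in the preceding off-treatment subperiod.

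PD needs no change. The cost is SAP wording and a PK-specific allocation condition, with no new data. The downside is that the PK on/off boundary would then differ from the Table 5 boundary shared with PDAI, PD, albumin and LDL-C. A footnote to the PK table should say so.
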